3.2 Investigational Product (device) and Indication

The IMD is a class IIa medical device. The brand name is Mermaid 9 S, manufactured by Bernafon AG. The software used to program the devices is Oasis^{next}. The device is intended for people with hearing loss that are over 36 months of age. The hearing aids are equivalent to those with CE Declaration of Conformity except that they contain an additional acoustical feedback cancellation algorithm. The device consists of a body made of plastic that houses the microphone(s), and chip. A speaker that is covered with a plastic dome is attached by a piece of thin plastic that goes over the ear. The plastic dome is the only part that is in contact with skin inside the ear canal. Only those trained as a hearing care professional in the fitting of hearing devices should program the device. However, anyone who receives a minimum amount of explanation concerning the use of the device is qualified to use it. The device is non-invasive and requires no surgical procedures.

3.3 Preclinical Evidence

Bernafon requires evidence of operational safety and medical effectiveness of the devices before testing them with human subjects. This evidence includes the device-related performance data in accordance with IEC 118-7: Measurement of the maximum output level and the maximum gain. In addition to the performance testing, the hearing aids are verified with system tests to ensure that they function according to the requirements. The safety of the fitting software is demonstrated by a beta version that has passed through a complete systematic software test and ensures the functionality of the hearing aids in combination with the software. Please see chapter B3e of the IB.

3.4 Clinical Evidence to Date

A clinical literature evaluation is maintained and has been updated in 2018. The basic benefit of hearing aids does not change with newly released devices. They are designed to amplify sound. The benefit of hearing aids has been shown in various studies (Kochkin, 2011). The evaluation includes an analysis of adverse events for Bernafon products as well as competitor devices and is used as post market analysis of the devices. The Mermaid 9 device was released to the market in early 2017. To date, there have been no adverse events reported on the U.S Food and Drug (FDA) Manufacturer and User Facility Device Experience (MAUDE) website.

A risk assessment is performed for all new devices. The primary risk identified is the possibility of over amplification from excessive sound pressure levels (further described in sec. 3.7). This risk is mediated by printing a warning in the Instructions for Use for hearing aids with high sound pressure level output capability. Additionally, when this type of instrument is selected in the software, there is a message warning the hearing care professional (HCP) of the sound pressure capability. Overall, Bernafon AG has had no adverse event reported in the last 16 years including no required modifications or recalls of products.

3.5 Medical Device: Rationale for the intended purpose in study (pre-market MD)

The IMD will be used in accordance with the current use of hearing devices. The intended purpose of the study is to compare the performance of the IMD with the RMD that is currently sold on the market. To make an effective comparison the test participants will wear the IMDs for approximately 10 days with a daily average use of 8-10 hours.

3.6 Explanation for choice of comparator (or placebo)

The comparison device will be the current equivalent Bernafon BTE style of hearing aid (RMD) that has

been available on the market since early 2017. The test participants will be fit with these devices during the trial to be able to compare them to the IMD. The reason for using the RMD is to control for performance differences caused by the new feedback cancellation system. Only changing the feedback system should, in theory, not adversely affect the performance of the device.

3.7 Risks / Benefits

A device risk analysis and risk assessment have been conducted for the new device according to EN ISO 14971. This describes the anticipated adverse device effects, residual risks associated with the investigational device and the procedures involved in its use. It also explains that the anticipated clinical benefit outweighs the potential risks. Please see the Risk Assessment for details.

The audiological and psychoacoustic investigations are conducted using volunteer test participants with sound pressure levels that will not endanger their residual hearing. The test participants will be advised of the type, content, extent, and possible risks of the test beforehand. As psychometric methods are involved in the data collection, the risk for the test participants is judged to be extremely minor. However, the following risks shall be addressed:

Risk of hearing loss to residual hearing at too high a level in audiological and psychoacoustic experiments: The hardware can provide an output that exceeds 132 dB SPL; however, only those with appropriate hearing loss (moderate to profound) will be fit with such devices reducing the risk to participants' residual hearing. During audiometry (test of hearing loss with audiometer) a level of more than 100 dB SPL must be used for test subjects who are profoundly hard of hearing. The risk is mitigated by the fact that the benefit of wearing hearing aids with a high output is higher than the risk to their minimal residual hearing.

Post-trial care is organized in a manner that allows the test participants to contact the sponsor site and arrange an appointment for any maintenance of their own devices as needed as they are all current hearing aid users.

3.8 Justification of choice of study population

The choice of study population was determined by the goal of the study. No minors or otherwise vulnerable participants will be included. The intended purpose of the study is to compare current Bernafon device performance with the existing feedback system against the new device with the new feedback system and not the overall effect of amplification. Therefore, only participants that are hearing impaired and experienced hearing aid users will be included. Bernafon has its own database of test subjects that are used for clinical trials. They are current hearing aid users that use the Bernafon clinic for adjustments to fittings and general maintenance of their hearing aids performed by the audiologists working at Bernafon. These test subjects do not consist of employees of Bernafon or family members of employees. The test subjects for the current study will be chosen from this internal subject database.

The comparison between devices shall be made with experienced hearing aid users. It is important to compare the performance of the devices and the subjective opinions of the intended users. Testing normal hearing participants would not contribute information to this study. Test participants must be able to sign and understand the consent form to be included in the study.

For emergency situations, the following applies:

The standard procedure is to recommend that a subject see the ENT with whom they have an established relationship. If a subject does not have an ENT then it is agreed with [name] (Inselspital, Bern) that, if necessary, subjects from the trial could be referred to him.

4. STUDY OBJECTIVES

4.1 Overall Objective

The purpose of this study is to evaluate whether the IMD provides a better feedback performance than the RMD. The study aims to provide a final validation and quality control of the IMD before it is released for sales.

4.2 Primary Objective

The study seeks to assess the performance of the new acoustic feedback cancellation system in comparison to the current feedback system. Scores from a live feedback test of the IMD will be compared to those of the RMD.

4.3 Secondary Objectives

Secondary objectives are to assess the performance of the IMD using speech testing and questionnaires (standardized and product). The performance of the IMD should not be inferior to that of the RMD.

4.4 Safety Objectives

The study aims to validate the overall implementation of the new feedback system by testing for unexpected behaviour from the IMD and to identify any new risk factors to ensure the safety of the devices before they are released to the market.

5. STUDY OUTCOMES

5.1 Primary Outcome

The primary outcome variable will be measured with a live feedback test that subjectively measures feedback annoyance that the participants experience in simulated real-life situations that typically elicit feedback. It will be measured in two conditions: aided with the RMD and aided with the IMD.

5.2 Secondary Outcomes

The secondary outcome will be measured with a standardized speech test and with questionnaires (standardized and product). The speech test will be measured in three conditions: unaided, aided with the RMD, and aided with the IMD. The questionnaires will be answered for both the RMD and the IMD, and then the answers compared. The product questionnaire will focus on the performance of the device with specific questions regarding feedback and sound quality. The Speech, Spatial, Quality (SSQ) questionnaire is a standardized questionnaire of overall performance and directly compares the RMD to the IMD.

5.3 Safety Outcomes

The product questionnaire that is used for the secondary outcome will also contain questions to measure the safety of the devices. These questions will specifically address unexpected noise or behaviour from the devices. Unexpected behaviour includes unprovoked feedback or whistling, distorted sounds or artefacts, spontaneous muting or shutting off of the device, and any unexplained warning signals, beeps, or loud sounds.

6. STUDY DESIGN

6.1 General study design and justification of design

This is a controlled, randomised, comparative clinical investigation conducted monocentric at the premises of Bernafon in Bern, Switzerland. The study will be conducted in three phases.

The exploratory study is based on a population of 33-55 hearing impaired people that have a hearing loss appropriate for the IMD. There are three phases of testing with the following minimum number of test participants required per phase: Phase 1 - 22, phase 2 - 22, phase 3 - 11. Participants from Phase 1 will have the option to also participate in Phase 2. If the same 22 test subjects participate in Phase 2, the total overall number of participants including those from Phase 3 will be 33. If an entire new group of 22 participate in Phase 2, the overall number will be 55.

As an RMD, the subjects will be fit with Mermaid 9 BTEs during the trial. Additionally, a control situation will be the unaided test condition for speech testing.

There is no placebo or device that does not provide amplification. The study is separated into three phases as each phase will test a specific hardware style that may react differently to the feedback cancellation system. The third phase will include a population with stronger hearing loss that requires more amplification and therefore, has a higher chance of experiencing feedback. For each phase, a single-group assignment design is used with test subjects that will be fit with the RMD and IMD during the trial. The field testing is unblinded as the difference between the IMD and the RMD is physically noticeable and obvious to the end user that it's different.

The first and second phases will consist of hearing impaired subjects with hearing loss ranging from mild to severe and appropriate for testing of the miniRITE-T and the miniRITE-T rechargeable hardware styles as well as the comparator miniRITE-T style. The third phase will consist of hearing impaired subjects with hearing loss ranging from moderate to profound and appropriate for the testing of the super power BTEs.

The lab testing (speech and feedback) will be blinded and randomised in a simulated environment. It is possible to blind the lab tests because the test subject will not place the hearing aids on their ears themselves. Before the lab testing begins they will hand over the hearing aids that they are wearing. As the PI will have the other set of hearing aids as well, they can discreetly choose the pair required by the randomisation list and place the hearing aids on the subjects without letting them see the devices. Once the devices are on/in the ears, there is no way to distinguish one style from the other. Feedback and speech testing conditions will be randomised. For the feedback tests, the test subjects will be tested in two aided conditions (comparator and IMD), and for speech, the test subjects will be tested in the unaided condition and two aided conditions. Speech tests will also be randomised by the word list.

The subjects in each phase are expected to participate for approximately 1 month. The participants from Phases 1 and 2 will have the option of participating in one or both phases of the study. The testing will include a combination of field and lab tests. There are two lab tests planned for each phase during which the participants will not spend more than 1.5 hours in the clinic (including breaks). The field test periods will not last more than 10 +/- 5 days.

The sequence for each phase of testing is the same. Each sequence will begin with the screening appointment in which participants are invited to the clinic for testing to determine if they are candidates for the trial. The entire test procedure will be explained, and they will be given a Patient Information and Informed Consent which will need to be signed, dated, and returned before any testing begins. If they choose to participate, a hearing test will be made to determine if they have an appropriate hearing loss and the RMD will be fitted.

The following appointments will include fitting of the IMD, two separate field tests during which they will wear the RMD (field test 1) and the IMD (field test 2), respectively, and lab tests in the clinic. There will be a total of 3 appointments, 1 before and after each field test, for each phase. Each appointment will not exceed 1.5 hours. During the lab tests in the clinic they will participate in live feedback testing and speech testing. Test subjects will be given questionnaires to complete at home and in the clinic.

After they have completed all appointments, the subjects will receive instructions about the continued use of their own hearing aids, and the reminder that they are welcome to come to the clinic for any maintenance or other follow-up of the hearing aids.

6.2 Methods of minimising bias

6.2.1 Randomisation

A single group assignment to the IMD will be used for the field trial. All subjects will wear the RMD for the first field test period and then the IMD for the second field test period. This procedure will be followed for all three phases. The lab tests, which include the live feedback test and the speech test, conducted in the clinic will be randomised. The live feedback and speech test order will be randomised based on a list created by the statistician. This means that for the live feedback and speech tests the subjects will be randomised by the hearing aid condition. This reduces bias by using a different starting and ending condition as the last condition has a higher chance of scoring higher due to a learning effect from the speech test. Additionally, the speech lists used for the speech test will be randomised as each list presents the same words but in different orders. The randomisation list will not be concealed from the PI but should be in the ISF so that the PI knows in which condition order to test each subject.

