6.2.2 Blinding procedures

The field tests will be unblinded as the differences in some of the hardware styles make it impossible to blind. As stated in section 6.2.1 all subjects will wear the RMD in the first field test period and the IMD in the second field test period. However, the lab tests in which feedback and speech are tested will be single blinded. In order to maintain the blind, the hearing aids will be taken from the subjects before the lab testing begins. They will be placed in the sound booth and seated in the middle of the speaker array. The PI will then enter the booth with the hearing aids hidden in their hand. The PI will approach the subjects from behind and place the hearing aids on the test subjects' ears without allowing them to see which hearing aids they are wearing during each testing session. The differences can be seen but not felt once the hearing aids are in position on the ears. The tubing and dome that fit in the ear canal are the same for each IMD style and their comparator; therefore, they will all feel the same to the subjects. The statistician will create a list to randomise the order of the blinded test condition using A and B to define which hearing aid (RMD or IMD) should be used for each round of tests. The PI will follow this list.

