7.3 Assignment to study groups

For the field tests the allocation is single group; therefore, all the test subjects will be assigned to the same group. The field test 1 will be with the RMD and the field test 2 with the IMD.

For the live feedback and speech tests in the lab, the assignment to the test condition order will be randomised by the statistician. The test condition order will be randomised using an A/B assignment. This will minimize bias created when one test condition is tested in the final or last position all the time.

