11.4.2 Primary Analysis

The live feedback test provides a measure of feedback annoyance on a visual analogue scale. A paired t-test will be used to evaluate if the observed difference (RMD - IMD) is higher than 0 in a first intention. However, the following factors are identified and should be included within a second analysis based on mixed-effect regression:

- Test device RMD vs IMD which is the main fixed effect,
- Participant as a random effect for the repeated measures, and the side (left-right) as nested random factor within participant,
- Feedback risk with the acoustical coupling, the hearing loss degree, and maximum gain measured from the REM,
- Manipulation as fixed effect.

The second analysis should provide more details about the dependencies between hearing loss degree, acoustical option and feedback annoyance.

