11.4.3 Secondary Analyses

Speech Test

Speech is measured with a standardized test called the WaKo Rhyme test from Wallenberg and Kollmeier (1989). The WAKO test is a closed word recognition test, i.e. one word is presented acoustically, and the subject must choose one answer out of five proposals. The outcome of each tested item is either 0 and 1 which can be modelled by a logistic mixed effect regression. Fixed effects are test condition, listening condition, hearing loss, i.e. 4- frequencies average of the best ear. Random effects are the participants and the tested item.

Product Questionnaire

Experienced acoustical feedback and sound quality are reported via a 5-points Likert scale. Differences between test conditions will be analysed with Wilcoxon signed-rank test.

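### The exploratory WaKo speech model has no test-position term, although condition order is randomised because the protocol expects learning across positions

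*Protocol*

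**What the plan says.** Section 6.2.1 has the statistician prepare a list that randomises the order of the hearing aid conditions for both lab tests. The reason given is that order should vary "as the last condition has a higher chance of scoring higher due to a learning effect from the speech test". The word lists are randomised too, and "each list presents the same words but in different orders", so words recur across conditions.

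The order list is described as "using A and B to define which hearing aid (RMD or IMD) should be used for each round of tests" (Section 6.2.2), and Section 7.3 says: "The test condition order will be randomised using an A/B assignment". But Section 6.1 says that "for speech, the test subjects will be tested in the unaided condition and two aided conditions". The protocol does not say where unaided falls in the order, and it neither promises nor excludes a balanced list.

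Section 11.4.3 specifies a logistic mixed model for the WaKo items. Its fixed part reads: "Fixed effects are test condition, listening condition, hearing loss, i.e. 4- frequencies average of the best ear". The random part of that model is given just as briefly: "Random effects are the participants and the tested item". Test position is not among these effects. The same section uses the term test conditions for the devices compared in the product questionnaire, so test condition there cannot be read as position.

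In the field part, everyone wears the RMD first and the IMD second, unblinded (Sections 6.2.1 and 6.2.2). The synopsis makes only the live feedback test confirmatory and everything else exploratory. Section 4.3 sets the aim that the IMD should not be inferior on speech testing and questionnaires.

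**The concern.** The protocol names a nuisance effect, guards against it in the design, and then fixes an analysis model that ignores it. Randomisation removes the bias on average, but a single phase has only 11 or 22 participants, and a list that is not balanced will by chance place one device later more often.

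The model counts many binary items per condition as independent, given participant and item. A participant intercept is the same in every test block, and the item effects recur from block to block. Neither picks up a lift that raises a whole block because it came later. The model's standard error therefore contains nothing for chance imbalance in order.

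WaKo is the blinded speech comparison behind the Section 4.3 aim. If its interval is too narrow, a difference due to test order can be read as a device difference.

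**Working it through.** **The plan's own figures.** The protocol gives no error rate, margin, item count or learning size for WaKo. Its only sample-size figures concern live feedback (Section 11.2), and they reproduce: effect size 1.54/1.63 = 0.945; n = 11 at 0.94 gives 80.2% power; n = 22 at 0.65 gives 82.8%, against 83% stated. This point does not touch them.

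**Inputs.** From the protocol: n = 22 (Phases 1 and 2) or 11 (Phase 3), three speech conditions, and the listed model effects. Assumed: learning L of 0.1 to 0.3 logit per position; 50 or 100 items per condition; about two thirds correct when aided. Near two thirds correct, L is about 2 to 6 percentage points per position. At L = 0.3 the lift from first to last is 0.6 logit, roughly 60% to 73%.

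**Hand calculation.** Let D be a participant's IMD position minus RMD position.

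- Six orders: D is ±1 in four and ±2 in two, so Var(D) = (4×1 + 2×4)/6 = 2.
- A/B with unaided first: D = ±1, so Var(D) = 1.
- Under simple randomisation the estimate gains a random shift with SD = L × √(Var(D)/n).
- If the model reports standard error s, the nominal 5% test rejects with probability 2Φ(−1.96 s / √(s² + L² Var(D)/n)).

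Take n = 22, 100 items and s = 0.069 (the mean model standard error in the simulation below):

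- Six orders, L = 0.3: shift SD = 0.3 × √(2/22) = 0.090; total = √(0.069² + 0.090²) = 0.114; rejection about 23.5%.
- A/B, unaided first, L = 0.3: shift SD = 0.3 × √(1/22) = 0.064; total 0.094; rejection about 15%.
- L = 0.1: about 7% and 6% respectively.

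Both s and the shift shrink with √n, so the larger phases are not better protected.

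**Simulation of the listed model.** 4,000 trials per cell; fixed condition, listening condition (two levels) and hearing loss; crossed random participant and item intercepts; penalised quasi-likelihood fit; Wald test at 1.96. Further assumptions: participant SD 0.6, item SD 0.5, unaided −1.0 logit, listening ±0.4, hearing loss −0.3 per SD, same words in every condition. The devices are truly equal. Rejection in %, without a position term, at L = 0.1 / 0.2 / 0.3:

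| Order list | n=11, 50 items | n=11, 100 items | n=22, 50 items | n=22, 100 items |
|---|---|---|---|---|
| Six orders, balanced | 4.9 / 5.0 / 5.5 | 4.7 / 6.5 / 7.0 | 5.0 / 4.9 / 5.0 | 4.9 / 5.3 / 5.8 |
| A/B simple-random, unaided first | 5.5 / 6.9 / 9.8 | 5.6 / 9.8 / 13.7 | 5.4 / 6.5 / 9.7 | 6.0 / 9.9 / 13.8 |
| Six orders, simple-random | 5.6 / 9.4 / 15.5 | 7.5 / 14.4 / 22.8 | 6.2 / 10.4 / 15.0 | 7.4 / 14.0 / 23.2 |

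With a position term, rejection is 4.3% to 5.5% under all three lists. Without learning it is 4.3% to 5.4% without the term and 4.0% to 5.4% with it. For six simple-random orders, n = 22, 100 items and L = 0.3, the contrast has an empirical SD of 0.112 against a mean model standard error of 0.069; with position, both are 0.071.

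**Second check.** A simpler simulation (contrast stratified by participant, no item effect, six simple-random orders, 50 items, L = 0.3) gave 12.7% falling to 3.9% with position at n = 22, and 12.4% falling to 4.2% at n = 11. The mean estimate stayed within about 0.005 logit of zero, so there is no bias. At L = 0.1 the rates without position were 5.4% and 4.8%.

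**The case against.** Randomised order and randomised word lists already deal with bias. What remains is the calibration of a standard error in an exploratory model for which the protocol sets no alpha, margin or decision rule; the 5% test is a yardstick chosen here. Learning size and item count are assumed throughout. At 0.1 logit, or with a balanced list, the effect is negligible or small. Section 17 lists a statistical plan that was not available, and the balance of an order list is often settled there. All of this stands, and it keeps the point modest. It does not remove it, because Section 11.4.3 names the model's effects itself and leaves out one that Section 6.2.1 asserts.

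A reader might infer more, and the documents do not support it:

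- **That the device contrast is biased.** It is not, because the order is randomised.
- **That 23% is the likely size.** It needs 0.3 logit, 100 items and six simple-random orders together. Sections 6.2.2 and 7.3 describe an A/B list, for which the maximum is about 14%, and they do not say that the list is unbalanced.
- **That the live feedback test shares the flaw.** Section 6.2.1 ties learning to the speech test, and no order effect on annoyance is stated. Neither the paired t-test nor the mixed model of Section 11.4.2 needs a position term on this ground.
- **That the fixed field order is a hidden error, or that the questionnaires must be barred from the Section 4.3 aim.** The order and the lack of blinding are openly declared and the outcomes are exploratory. Only a limit on interpretation follows.

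**Conclusion.** The point holds as a modest one. The WaKo model omits a position effect that the protocol expects. The estimate stays unbiased, but its interval is too narrow if learning is material and the order list is unbalanced. Under the stated assumptions, nominal 5% becomes about 5% to 14% with a simple-random A/B list and unaided first, up to about 23% with six simple-random orders, and about 5% to 7% with a balanced list. A position term restores about 5%. The size rests wholly on the assumed learning and item counts.

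Separately, device and period are the same variable within a phase for the field-based product questionnaire, SSQ and preference results. A period effect there passes straight into the device difference, and no model term can remove it.

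**What to change.** 1. **Section 11.4.3:** add the test position of the device condition (first, second, third) as a fixed effect in the exploratory WaKo model. Position should refer to the device condition, so that it stays defined if each condition is tested in more than one listening condition. If unaided is always first, use the order of the two aided conditions instead, because position one then coincides with unaided.
2. **Section 6.2.1:** state that the statistician's speech order list is balanced within each phase, as nearly as 22 or 11 participants allow, and where the unaided condition falls.
3. **Reporting of the product questionnaire, SSQ and preference results:** add the caveat that device and period coincide and wear is unblinded, so differences cannot be attributed to the device alone.
4. **Live feedback:** leave the analysis and its order list as they are.

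The cost is wording and two degrees of freedom (one if only the aided order is used); position can be read from the list already planned. With no learning and a true difference of 0.3 logit, power at 50 items under a balanced list goes from 55.7% to 56.0% (n = 11) and from 84.7% to 84.6% (n = 22). With six simple-random orders it falls from 55.8% to 52.1% and from 84.7% to 82.6%, and with n = 11 and 100 items from 84.7% to 80.0%. This is why items 1 and 2 belong together.
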